8.3.6 Adverse event of special interest

Adverse event of special interest

An AESI is an AE (serious or nonserious) of scientific and medical concern specific to the Sponsor's product or program, for which ongoing monitoring and immediate notification by the Investigator to the Sponsor is required. Such events may require further investigation in order to characterize and understand them. Adverse events of special interest may be added, modified, or removed during a study by protocol amendment. For these AESIs, the Sponsor will be informed immediately (ie, within 24 hours), per SAE notification described in [Section 10.3](#), even if not fulfilling a seriousness criterion, using the corresponding screens in the eCRF.

AESIs for this study include:

- Anaphylactic reactions.
- Systemic hypersensitivity reactions.
- Helminthic infections.
- Any severe type of conjunctivitis or blepharitis.

- Keratitis.
- Clinically symptomatic eosinophilia (or eosinophilia associated with clinical symptoms).
- Pregnancy of a female participant entered in a study as well as pregnancy occurring in a female partner of a male participant entered in a study with IMP
 - Pregnancy occurring in a female participant entered in the clinical trial or in a female partner of a male participant entered in the clinical trial. It will be qualified as an SAE only if it fulfills one of the seriousness criteria.
 - In the event of pregnancy in a female participant, IMP should be discontinued.
 - Follow-up of the pregnancy in a female participant or in a female partner of a male participant is mandatory until the outcome has been determined.
 - Abnormal pregnancy outcomes (eg, spontaneous abortion, fetal death, stillbirth, congenital anomalies, ectopic pregnancy) are considered SAEs.
- Significant ALT elevation
 - ALT $>5 \times$ ULN in participants with baseline ALT $\leq 2 \times$ ULN;
OR
 - ALT $>8 \times$ ULN if baseline ALT $>2 \times$ ULN.
- Symptomatic overdose (serious or nonserious) with IMP
 - An overdose (accidental or intentional) with the IMP is an event suspected by the Investigator or spontaneously notified by the participant and defined as at least twice the maximum prescribed daily dose, within the intended therapeutic interval. “The circumstances (ie, accidental or intentional) should be clearly specified in the overdose form”.

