10.3.3 Recording and follow-up of AE and/or SAE

AE and SAE recording

- When an AE/SAE occurs, it is the responsibility of the Investigator to review all documentation (eg, hospital progress notes, laboratory reports, and diagnostics reports) related to the event.
- The Investigator will then record all relevant AE/SAE information in the eCRF.
- It is **not** acceptable for the Investigator to send photocopies of the participant's medical records to the Sponsor's representative in lieu of completion of the AE/SAE eCRF page.
- There may be instances when copies of medical records for certain cases are requested by the Sponsor's representative. In this case, all participant identifiers, with the exception of the participant number, will be redacted on the copies of the medical records before submission to the Sponsor's representative.

- The Investigator will attempt to establish a diagnosis of the event based on signs, symptoms, and/or other clinical information. Whenever possible, the diagnosis (not the individual signs/symptoms) will be documented as the AE/SAE.

Assessment of intensity

The Investigator will make an assessment of intensity for each AE and SAE reported during the study and assign it to 1 of the following categories:

- Mild: An event that is easily tolerated by the participant, causing minimal discomfort and not interfering with everyday activities.
- Moderate: An event that causes sufficient discomfort and interferes with normal everyday activities.
- Severe: An event that prevents normal everyday activities. An AE that is assessed as severe should not be confused with a SAE. Severe is a category utilized for rating the intensity of an event; and both AEs and SAEs can be assessed as severe.

An event is defined as “serious” when it meets at least 1 of the predefined outcomes as described in the definition of an SAE, NOT when it is rated as severe.

Assessment of causality

- The Investigator is obligated to assess the relationship between study intervention and each occurrence of each AE/SAE.
- A “reasonable possibility” of a relationship conveys that there are facts, evidence, and/or arguments to suggest a causal relationship, rather than a relationship cannot be ruled out.
- The Investigator will use clinical judgment to determine the relationship.

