- Any TEAE leading to permanent intervention discontinuation
- Any treatment-emergent AESI
- Any treatment-emergent other AE of interest grouping
- Any TEAE related to IMP

The AE summaries of **Table 5** will be generated with number (%) of participants experiencing at least one event. A separate analysis of TEAE by primary SOC and PT will be provided for pediatric patients.

Table 5 - Analyses of adverse events

Type of AE	MedDRA levels
All TEAE	Primary SOC, HLGT, HLT and PT
	Primary SOC and PT
	Primary SOC
	PT
Common TEAE ($\geq 5\%$ in any group)	Primary SOC and PT
TEAE related to IMP as per Investigator's judgment	Primary SOC, HLGT, HLT and PT
	Primary SOC and PT
TEAE by maximal intensity	Primary SOC and PT
Treatment emergent SAE	Primary SOC, HLGT, HLT and PT
	Primary SOC and PT
Treatment emergent SAE related to IMP as per Investigator's judgment	Primary SOC and PT
TEAE leading to permanent intervention discontinuation	Primary SOC, HLGT, HLT and PT
	Primary SOC and PT
TEAE leading to death ^b	Primary SOC, HLGT, HLT and PT
	Primary SOC and PT
Pretreatment AE	Overview ^a
	Primary SOC and PT
Post-treatment AE	Overview ^a
	Primary SOC and PT
Post-treatment SAE	Primary SOC and PT

^a Will include the following AE categories: any AEs, any serious AEs, any AEs leading to death, any AEs leading to permanent intervention discontinuation

^b Death as an outcome of the AE as reported by the Investigator in the AE page

Analysis of deaths

In addition to the analyses of deaths included in Table 5 the number (%) of participants in the following categories will be provided:

- Deaths during the treatment-emergent and post-treatment periods by main reason for death
- Deaths in non-randomized participants or randomized but not treated participants

Analysis of adverse events of special interest (AESIs) and other AEs of interest

Adverse events of special interest (AESIs) and other AEs of interest will be selected for analyses as indicated in [Table 6](#). Number (%) of participants experiencing at least one event will be provided for each event of interest, by PT if applicable. Tables will be sorted as indicated in [Table 4](#).

Table 6 - Selections for AESIs and other AEs of interest

AESIs and other AEs of interest	Selection
AESI	

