Anaphylactic reaction	Anaphylactic reaction algorithmic approach (Introductory Guide for Standardized MedDRA Queries (SMQs) Version 18.1): includes anaphylactic reaction narrow SMQ (20000021) terms and programmatic identification of cases based on occurrence of at least two preferred terms meeting the algorithm criteria occurring within 24 hours of each other. The latter cases identified using the algorithm will undergo blinded medical review taking into account the timing of events relative to each other and to IMP administration for final determination of an anaphylactic reaction or not.
Systemic hypersensitivity reactions	SMQ [20000214] hypersensitivity narrow search and [AE corrective treatment/therapy = 'Y' or Action taken with IMP = 'Drug withdrawn' or Action taken with IMP = 'Drug interrupted'] followed by blinded medical review (documented process) for selection of relevant systemic hypersensitivity events
Helminthic infections	CMQ10544 based on HLGT as "Helminthic disorder"
Any severe type of conjunctivitis	CMQ10498 based on PTs (See Appendix 6) ^a and "Severe" ticked in Adverse Events eCRF page
Any severe type of blepharitis	CMQ10497 based on HL as "Lid, lash and lacrimal infections, irritations and inflammations" and "Severe" ticked in Adverse Events eCRF page
Keratitis	CMQ10642 based on the following PTs [keratitis, allergic keratitis, ulcerative keratitis, atopic keratoconjunctivitis, herpes ophthalmic, ophthalmic herpes simplex, corneal infection] ^a
Clinically symptomatic eosinophilia (or eosinophilia associated with clinical symptoms) ^b	CMQ10641 based on HL = Eosinophilic disorders or PT = Eosinophil count increased followed by blinded medical review
Pregnancy of female participants entered in a study as well as pregnancy occurring in a female partner of a male participant entered in a study with IMP	"Pregnancy" or "Partner Pregnancy" checked on the Pregnancy eCRF page as reported by the investigator

AESIs and other AEs of interest	Selection
Significant ALT elevation	"ALT increase" and AESI answer "Yes" checked on AE eCRF as reported by the Investigator (ALT >5 × ULN in participants with baseline ALT ≤2 × ULN; OR ALT >8 × ULN if baseline ALT >2 × ULN)
Symptomatic overdose with IMP	Symptomatic Overdose is answered Yes, with Overdose of Study Treatment answered Yes on AE eCRF.
Other selected AE Grouping	

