- Number (%) of participants with any AE leading to death
- Number (%) of participants with any TEAE leading to permanent study intervention discontinuation
- Number (%) of participants with any TEAE related to IMP reported by investigator
- Number (%) of participants with any TEAE by maximum intensity, corrective treatment, and final outcome
- Number (%) of participants with any TEAE adjusted by the exposure duration
- Number (%) of participants with injection site reactions by the related injection.
- Number (%) of participants with different number of injection site reactions.

In addition, AESIs reported by the investigator in eCRF will be summarized separately.

Analysis of exposure-adjusted incidence rate

If the cumulative duration of treatment exposure is imbalanced between dupilumab and placebo, then the number of participants with at least one TEAE per 100 participant-years will be provided for the below summaries:

- Overview of adverse events profile
- TEAE by primary SOC and PT
- Common TEAE ($\geq 5\%$ in any group) by primary SOC and PT
- Treatment-emergent SAE by primary SOC and PT
- TEAE leading to permanent intervention discontinuation by primary SOC and PT
- Treatment-emergent AESI and other selected AE grouping events by category and PT

For participants with an event, the number of participant-years will be censored at time of the first event; for participants without an event, the number of participant-years corresponds to the length of the treatment-emergent period.

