Analyses according to PCSA will be performed based on the worst value during the treatment-emergent period, using all measurements (either local or central, either scheduled, nonscheduled or repeated).

For laboratory variables and vital signs above, the incidence of participants with at least one PCSA during the treatment-emergent period will be summarized regardless of the baseline level and according to the following baseline status categories:

- Normal/missing
- Abnormal according to PCSA criterion or criteria

Additional analyses for drug-induced liver injury

The following additional analyses will be performed for potential drug-induced liver injury:

- Time to onset of the initial alanine aminotransferase (ALT) or aspartate aminotransferase (AST) elevation ($>3 \times \text{ULN}$) and total bilirubin elevation ($>2 \times \text{ULN}$) during the treatment-emergent period will be analyzed using Kaplan-Meier method.
- A graph of the distribution of peak values of ALT versus peak values of total bilirubin during the treatment-emergent period will be provided.
- For each liver function test (eg, ALT), participants having experienced a PCSA (eg, ALT $>5 \text{ ULN}$) will be summarized using the following categories: Returned to baseline PCSA status (or returned to value $\leq \text{ULN}$ in case of missing baseline) before last IMP dose, Returned to baseline PCSA status after last IMP dose, Never returned to baseline PCSA status, No assessment after elevation. This summary will be performed by categories of elevation (ALT $>3, >5, >10, >20 \text{ ULN}$).

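### SAP Table 6 identifies the ALT elevation AESI only from the investigator's AE-form entry, although protocol 8.3.6 gives measured-ALT thresholds for it

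*SAP*

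**What the plan says.** Protocol 8.3.6 lists "Significant ALT elevation" as an AESI with two limbs. ALT must exceed 5 x ULN if baseline ALT is at most 2 x ULN, or exceed 8 x ULN if baseline ALT is above 2 x ULN. Protocol 9.4.5 leaves the method of identifying AESIs to the SAP.

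SAP 3.6.2 states: "Adverse events of special interest (AESIs) and other AEs of interest will be selected for analyses as indicated in" Table 6. The ALT row of that table requires an ALT increase entry and "AESI answer 'Yes' checked on AE eCRF as reported by the Investigator". The thresholds follow in parentheses: "ALT >5 × ULN in participants with baseline ALT ≤2 × ULN; OR ALT >8 × ULN if baseline ALT >2 × ULN". The row names no search of the laboratory data.

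After the Table 6 summaries, the same section adds: "In addition, AESIs reported by the investigator in eCRF will be summarized separately".

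Measured ALT is analysed in SAP 3.6.3.1. That section has PCSA incidence from all local and central values, a plot of peak ALT against peak bilirubin, and a summary of whether liver-test abnormalities resolved. Of the last it says "This summary will be performed by categories of elevation", with ALT cuts at 3, 5, 10 and 20 x ULN.

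**The concern.** The protocol gives this event a numerical definition, and the data needed to apply it are in the database. The SAP nevertheless finds the event through a form entry. A count built that way depends partly on how sites complete the form.

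An entry could be absent in three ways:

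- Under protocol 10.3.1 a laboratory abnormality becomes an AE when the investigator judges it clinically significant, so an elevation might not be entered at all.
- An AE might be entered with the AESI question left unanswered.
- Protocol 10.3.3 instructs: "Whenever possible, the diagnosis (not the individual signs/symptoms) will be documented as the AE/SAE". An elevation that forms part of a liver diagnosis might therefore be entered under the diagnosis and not as an ALT increase.

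At stake is the accuracy of one AESI row and of the overview line that includes it. For most of the other medical AESIs, Table 6 uses coded-term searches that do not need the AESI tick, so the separate investigator-reported summary offers a comparison. For ALT both outputs rest on the same entry, and that comparison is lost.

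**Working it through.** The plan states no figure to reproduce. The check sets the passages side by side and adds one line of arithmetic for scale.

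**Step 1. Which participants does Table 6 count?** The parenthetical thresholds can be read as a description of what the investigator should have ticked (reading 1) or as a condition enforced in addition to the tick (reading 2). 'Ticked' means that both the ALT increase entry and the AESI answer are present.

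| Measured ALT meets 8.3.6 | Ticked | Counted, reading 1 | Counted, reading 2 |
|---|---|---|---|
| yes | yes | yes | yes |
| yes | no | no | no |
| no | yes | yes | no |
| no | no | no | no |

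The second line is the gap, and it is there on both readings, because an added condition can only narrow the ticked cases. The third line is a possible over-count on reading 1 only.

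**Step 2. Does another AESI output recover the second line?** The separate summary of investigator-reported AESIs rests on the same source, so it does not. The overview line for any treatment-emergent AESI would include the participant only through some other AESI.

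**Step 3. Where would such a participant still be seen?**

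- *Recovery summary.* Both limbs lie above 5 x ULN, so every qualifying participant belongs in the >5 x ULN category. That category also holds participants with baseline above 2 x ULN and a peak above 5 but not above 8 x ULN, who do not qualify. Everyone above 10 x ULN qualifies on either limb. If the categories are cumulative and cover all participants, then:

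  number >10 x ULN ≤ number meeting 8.3.6 ≤ number >5 x ULN

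  The printed categories have no 8 x ULN cut and no split at baseline 2 x ULN, so they bound the AESI count without giving it.
- *Peak ALT plot.* The value would be shown, without an AESI label.
- *PCSA incidence.* It uses measured values, but the criteria come from a sponsor list that the SAP does not print, so its cuts cannot be checked here.
- *Drug-related hepatic disorder, narrow SMQ (Table 6, other groupings).* It needs no AESI tick and could pick up a case coded as a liver diagnosis. It searches recorded AE terms, not ALT values, and is not an AESI.

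**Step 4. Scale.** Protocol 4.1 plans 31 participants per arm.

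- One missed participant: 1/31 = 0.032, or 3.2 percentage points of that arm.
- The documents give no expected frequency. Assuming 0 to 2 missed cases, all in one arm, the row would be low by 0, 3.2 or 2/31 = 6.5 percentage points.

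**The case against.** The strongest defence is that the SAP contradicts nothing. Protocol 8.3.6 describes an AESI as a kind of adverse event that the investigator must notify, and the identification method was left to the SAP. Counting reported events is a legitimate choice, and Table 6 does the same for pregnancy, symptomatic overdose, and parasitic and opportunistic infections. This stands: the point is a weakness in a permitted choice, not a conflict between the documents. Nor do the documents state that Table 6 is meant to be a sponsor selection independent of the investigator.

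The safeguards are also real. The same thresholds appear in protocol 7.1.1 among the reasons for withdrawal from study treatment, and such withdrawals are recorded in the eCRF. Protocol 8.2.4 requires investigators to review each laboratory report and record clinically relevant changes as AEs. AESIs must be notified within 24 hours. A qualifying elevation that nobody recognises is unlikely, although a recognised one with an incomplete form entry remains possible.

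A reader might infer two stronger things that the documents do not support:

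- *That measured ALT elevations would go unreported.* SAP 3.6.3.1 analyses them from the laboratory data.
- *That the ALT row can only under-count.* On reading 1 a below-threshold tick would be counted, so the error can go either way.

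The eCRF is not available, so it cannot be settled whether the ALT increase entry is a fixed field or free text, or how often a diagnosis would displace it.

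**Conclusion.** The point holds, at low severity. Under either reading of Table 6, a participant whose measured ALT meets the protocol thresholds without the investigator's entry is left out of the ALT AESI row, and no other AESI output restores the case. Nothing in the documents shows that any such case exists; the finding concerns what would happen if one did.

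The consequence is a wrong AESI label or count, since the measured elevation still reaches the laboratory outputs. Because the event is expected to be rare (an assumption), a single discordant case could change the row from one event to none. SAP 3.6 describes the safety analysis as essentially descriptive with no testing, and no efficacy conclusion is affected.

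**What to change.** Change the ALT row of Table 6 so that the event is selected when either condition is met:

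1. any ALT in the treatment-emergent period, central or local, meets the protocol 8.3.6 thresholds against the participant's baseline; or
2. the investigator recorded the ALT increase and ticked the AESI question.

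Add a listing of discordant cases in both directions: threshold met but not ticked, and ticked with no value above the threshold. Leave the investigator-only count in the separate summary that SAP 3.6.2 already plans, so that the two sources can be compared for ALT as well.

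The cost is one derivation and one short listing from laboratory data already collected. The AESI count may come out slightly higher than under the present rule.

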Systemic hypersensitivity is established as an important identified risk with dupilumab. As protein therapeutics, all monoclonal antibodies are potentially immunogenic. Rare serious and systemic hypersensitivity reactions have been observed in the dupilumab program including serum sickness/serum sickness-like reaction in the adult AD program and anaphylaxis related to dupilumab in the adult asthma clinical trials.

The important potential risk for dupilumab is “eosinophilia associated with clinical symptoms in asthma patients.” The observed increase in eosinophil count is transient, which is consistent with the current understanding of the mechanism of action of dupilumab. In dupilumab asthma studies, a small number of patients with asthma experienced serious systemic eosinophilia presenting with clinical features of eosinophilic pneumonia or vasculitis consistent with eosinophilic granulomatosis with polyangiitis, conditions which are often treated with SCS therapy. These events have been seen in other drug development programs for severe asthma and usually, but not always, have been associated with the reduction of oral corticosteroid therapy suggesting possible unmasking of these conditions with tapering of corticosteroids during dupilumab therapy. The association of dupilumab treatment and these events has not been established. Health care providers should be alert to eosinophilia associated with vasculitic rash, worsening of pulmonary symptoms, pulmonary infiltrate, cardiac complications, and/or neuropathy presenting in their participants, especially upon reduction of SCS.

Patients with known helminth infections were excluded from participation in clinical studies, therefore it is not known if dupilumab will influence the immune response against helminth infections. Consequently, patients with pre-existing helminth infections should be treated for their helminth infection before initiating therapy with dupilumab.

The common ADR across all indications is injection site reactions. Other potential risks based on the safety profile in particular indications are discussed in the IB.

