9.4.5 Other safety analyses

All safety analyses will be performed on the safety population. The summary of safety results will be presented by treatment group. The baseline value is defined generally as the last available value before first dose of IMP.

Adverse event incidence tables will present by system organ class (SOC) (sorted by internationally agreed order) and preferred term (PT), the number (n) and percentage (%) of participants experiencing an AE. Multiple occurrences of the same event in the same participant will be counted only once in the tables within a treatment phase. The denominator for computation of percentages is the safety population within each treatment group.

Proportion of participants with at least 1 treatment-emergent adverse event (TEAE), treatment-emergent SAE, TEAE leading to death, and TEAE leading to permanent treatment discontinuation will be tabulated by treatment group. In addition, TEAEs will be described according to maximum intensity and relation to the study intervention. Serious AEs and AEs leading to study discontinuation that occur outside the treatment-emergent period will be summarized separately.

Incidence of each type of AESI and other AE groupings will be tabulated by treatment group. For each type of AESI, the following analysis will be generated.

A summary of the number (%) of participants with

- Any TEAE.
- Any SAE (regardless of treatment-emergent status).
- Any treatment-emergent SAE.
- Any AE leading to death.
- Any TEAE leading permanent treatment discontinuation.
- Any TEAE related to study intervention reported by the Investigator.
- Any TEAE by maximum intensity, corrective treatment, and final outcome.

The method to identify AESIs and other AE groupings will be specified in the SAP.

The following deaths summaries will be generated:

- Number (%) of participants who died by study period (TEAE, on-study) summarized on the safety population by treatment received.
- Death in nonrandomized participants or randomized and not treated participants.
- TEAE leading to death (death as an outcome on the AE eCRF page as reported by the Investigator) by primary SOC and PT showing number (%) of participants.

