Serious injection site reactions or severe injection site reactions that last longer than 24 hours	HLT = 'Injection site reactions' and either with serious status, or with severe status and (AE end date/time - AE start date/time) ≥24 hours or ongoing
Severe or serious infection	Primary SOC = 'Infections and infestations' and with severe or serious status
Parasitic infection	Infection type "Parasitic" checked on eCRF "Infection Event Form"
Opportunistic infection	Has the AE been assessed as opportunistic infection? is answered Yes on eCRF "Infection Event Form"
Drug-related hepatic disorder	SMQ [20000006] Drug-related hepatic disorders- narrow
Injection site reactions	HLT = 'Injection site reactions'
Malignancy	SMQ [20000091]- Malignant or unspecified tumors narrow
Conjunctivitis (narrow)	CMQ10644 based on the following PTs [Conjunctivitis, Conjunctivitis allergic, Conjunctivitis bacterial, Conjunctivitis viral, Atopic keratoconjunctivitis] ^a
Conjunctivitis (broad)	CMQ10645 based on the following PTs [Conjunctivitis, Conjunctivitis allergic, Conjunctivitis bacterial, Conjunctivitis viral, Atopic keratoconjunctivitis, Blepharitis, Dry eye, Eye irritation, Eye pruritus, Lacrimation increased, Eye discharge, Foreign body sensation in eyes, Photophobia, Xerophthalmia, Ocular hyperaemia, Conjunctival hyperaemia] ^a
Conjunctivitis (FDA) ^c	CMQ10643 based on the following PTs [Conjunctivitis, Conjunctivitis allergic, Conjunctivitis bacterial, Conjunctivitis viral, Eye irritation, Eye inflammation, Giant papillary conjunctivitis] ^a
Keratitis (FDA) ^c	CMQ30102 based on the following PTs [keratitis, allergic keratitis, ulcerative keratitis, atopic keratoconjunctivitis, ophthalmic herpes simplex] ^a

a The list of terms may be adjusted according to MedDRA version changes

b All cases of Eosinophilia will be included in the analysis, where cases associated with clinical symptoms will be further described in the CSR

c Labeling subgroup of preferred terms included in the USPI for Dupixent.

The following summaries will be provided:

- All TEAEs, by selected standardized MedDRA query (SMQ)/Customized MedDRA query (CMQ) and PT, showing the number (%) of participants with at least 1 PT.
- For each AESI and other selected AE groupings,
 - Number (%) of participants with any TEAE
 - Number (%) of participants with any serious AE (regardless of treatment-emergent status)

- Number (%) of participants with any treatment-emergent serious AE

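### The AESI row for clinically symptomatic eosinophilia is set to count all eosinophilia adverse events, which is wider than the protocol's definition

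*SAP*

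**What the plan says.** Protocol 8.3.6 lists the AESI as "Clinically symptomatic eosinophilia (or eosinophilia associated with clinical symptoms"), so symptoms are part of the definition. Protocol 9.4.5 leaves the search to the SAP: "The method to identify AESIs and other AE groupings will be specified in the SAP".

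SAP 3.6.2, Table 6, carries the same symptomatic label under its AESI heading and gives this selection: "CMQ10641 based on HL = Eosinophilic disorders or PT = Eosinophil count increased followed by blinded medical review". Footnote b, attached to that row, adds: "All cases of Eosinophilia will be included in the analysis, where cases associated with clinical symptoms will be further described in the CSR".

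AESIs then feed several outputs in SAP 3.6.2: the overview line "Any treatment-emergent AESI", the set of summaries produced for each AESI, and the exposure-adjusted rates that are produced if exposure is imbalanced between arms. The same section also plans a separate summary of AESIs as reported by the investigator.

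**The concern.** A row headed as symptomatic eosinophilia should contain symptomatic cases. Under footnote b it contains every eosinophilia adverse event that the search finds. The reader of the safety tables would take the row as the incidence of the protocol's AESI when it is the incidence of something broader.

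This matters for two reasons. Protocol 2.3.2 names eosinophilia with clinical symptoms, in asthma patients, as the important potential risk for dupilumab, so this count will be looked at. The same section says of the drug: "The observed increase in eosinophil count is transient, which is consistent with the current understanding of the mechanism of action of dupilumab". It also lists eosinophilia, with no symptom qualifier, among the identified adverse drug reactions. Asymptomatic cases may therefore occur more often on dupilumab, and mixing them with symptomatic ones would blur the comparison that the AESI exists to show.

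**Working it through.** The documents state no figure on this point, so there is nothing to reproduce. The check is a comparison of texts plus one division.

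**1. Definition against counting rule.**

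| Source | What counts |
|---|---|
| Protocol 8.3.6 | Eosinophilia with clinical symptoms |
| SAP Table 6, row label | The same |
| SAP Table 6, selection | Events coded to eosinophilic disorders or to an increased eosinophil count, then blinded review |
| SAP Table 6, footnote b | All eosinophilia cases |

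The last line is wider than the first two. Protocol 9.4.5 delegates how AESIs are identified. It does not say that the SAP may change what the AESI is. The SAP's Version History, which lists modifications from the protocol's statistical section, does not mention a widening.

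**2. Role of the blinded review.** The systemic hypersensitivity row states its purpose: "followed by blinded medical review (documented process) for selection of relevant systemic hypersensitivity events". The anaphylaxis row likewise says that the review makes the final determination. The eosinophilia row stops at "Eosinophil count increased followed by blinded medical review". If the review is meant to filter the row, footnote b contradicts it. If it is not, the row label is wrong.

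**3. What reaches the row.** The search runs on coded adverse events. Under Protocol 10.3.1 an abnormal laboratory result is an adverse event only if the investigator judges it clinically significant. That filter removes many laboratory rises, but clinically significant is not the same as symptomatic, so asymptomatic events can still enter.

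**4. Weight of one participant.** Protocol 4.1 plans 31 per arm. The true denominator is the safety population; I assume that all 31 are treated.

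- One extra participant: 1/31 = 3.2 percentage points.
- The any-AESI line moves by the same amount only if that participant has no other AESI.

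**5. Range.** The documents give no rate of asymptomatic eosinophilia adverse events. Assumed counts in one arm:

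| Extra participants (assumed) | Added to that arm's row |
|---|---|
| 0 | 0 |
| 1 | 1/31 = 3.2 points |
| 3 | 3/31 = 9.7 points |
| 5 | 5/31 = 16.1 points |

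If only confirmed symptomatic cases were counted, the addition would be 0 in every line.

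**The case against.** The strongest reply is that this is a disclosed presentation choice that errs towards including too much. The protocol leaves the method to the SAP, eosinophilia of any kind is a listed adverse drug reaction, and the broad rule is printed under the table. Investigators report this AESI under the protocol's symptomatic definition, and those reports get their own summary, so a count close to the narrow definition is already planned. Results are also split by preferred term where applicable, and by seriousness, intensity, corrective treatment and outcome. Eosinophil values are analysed separately as laboratory data (SAP 3.6.3.1).

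Most of this stands, and it limits the consequence. It does not remove the mismatch. The investigator-reported summary is not the result of the blinded review, so two tables carrying the same AESI label could disagree with no stated reason.

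Three stronger readings are tempting, and the documents do not support them:

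- *Asymptomatic laboratory rises are reported as AESIs.* Only rises that were reported as adverse events and coded to these terms are counted.
- *The blinded review does nothing, and symptomatic cases are hidden.* Footnote b itself separates symptomatic cases, so someone must classify them, and the review is the natural means. Saying that they will be described in the CSR does not exclude a count. The gap is that no purpose and no count are committed to.
- *The rule inflates the dupilumab arm.* Protocol 2.3.2 makes that direction plausible, but it gives no rate, the rule applies to both arms, and the review is blinded.

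**Conclusion.** The inconsistency is real and minor. Read as written, footnote b brings events outside the protocol's AESI into a row that carries the AESI's name and, because Table 6 defines the AESI selection, into the any-AESI line. The plan does not commit to a by-arm count of review-confirmed symptomatic cases.

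The only size that the documents support is 3.2 percentage points per affected participant, assuming 31 treated per arm. The number of such participants is unknown and could be zero. SAP 3.6 makes the safety analysis descriptive with no testing, so no type I error, power or efficacy conclusion is affected.

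**What to change.** Edit SAP Table 6 before unblinding:

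1. State that the blinded medical review classifies each case found by the search as symptomatic or not.
2. Count only confirmed symptomatic cases in the AESI row, its sub-summaries and the any-AESI line.
3. Add all eosinophilia (CMQ10641) as its own row under *Other selected AE Grouping*.
4. Reword footnote b to match.

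The SAP already handles conjunctivitis this way: severe cases form the AESI and the broader groupings sit lower in the table. If the sponsor prefers to keep the broad row, an alternative is to relabel it as all eosinophilia, add a symptomatic sub-row, and say which of the two feeds the any-AESI line.

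The review is already planned, so the cost is a table edit and one extra row. The AESI count may come out lower, but the broad count stays visible in its own row.
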